7.1.2. Planned Efficacy Statistical Analyses

Primary Statistical Analyses
Endpoint(s)

 Change from Baseline in HbA_{1c} at Week 26
Model Specification

 Change from Baseline in HbA_{1c} = Baseline HbA_{1c} + Treatment + Region + Age Category + Current Use of Metformin + Visit Week + Treatment-by-Visit Interaction + Baseline HbA_{1c}-by-Visit Week Interaction (Model 1)
Model Checking & Diagnostics

 Refer to Appendix 11: Model Checking and Diagnostics for Statistical Analyses
Model Results Presentation

 The least squares mean of the treatment difference at Week 26 estimated from the MMRM model and its 1-sided 97.5% confidence interval Descriptive statistics for the observed HbA_{1c} and change from Baseline HbA_{1c} Plot of the least squares means (and standard errors) of change from Baseline HbA_{1c} by treatment group Refer to Appendix 14: List of Data Displays
Supportive Statistical Analysis

 The generalizability of the treatment effect will be evaluated within a supportive MMRM model that adds terms for treatment-by-variable interaction. The variables include baseline HbA_{1c}, region, age category, and current use of metformin. The primary endpoint will also be analyzed using Model 1 above in the Per-Protocol Population
Model Specification

 Change from Baseline in HbA_{1c} = Baseline HbA_{1c} + Treatment + Region + Age Category + Current Use of Metformin + Visit Week + Treatment-by-Visit Interaction + Baseline HbA_{1c}-by-Visit Week Interaction + Treatment-by-Variable + Visit Week-by-Variable + Treatment-by-Visit Week-by-Variable. Refer to Appendix 11: Model Checking and Diagnostics for Statistical Analyses for SAS code
By-Subgroup Statistical Analysis

 The subgroup analyses will be performed using MMRM models. The subgroups include baseline HbA_{1c} category, gender, race, ethnicity, age category, baseline BMI category, region, duration of diabetes category and current use of metformin. Refer to Appendix 9: Examination of Covariates, Subgroups & Other Strata.
Model Specification

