
 Change from Baseline in HbA_{1c} = Baseline HbA_{1c} + Treatment + Region + Age Category + Current Use of Metformin + Visit Week + Treatment-by-Visit Interaction + Baseline HbA_{1c}-by-Visit Week Interaction+ Treatment-by-Visit Week-by-Variable + Treatment-by-Variable + Visit Week-by-Variable. Refer to Appendix 11: Model Checking and Diagnostics for Statistical Analyses for SAS code
Sensitivity Statistical Analysis with Respect to Missing Data MAR Assumption

 Refer to Appendix 6, Section 11.6.3: Sensitivity Analysis on the Primary Efficacy Endpoint

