11.11. Appendix 11: Model Checking and Diagnostics for Statistical Analyses

11.11.1. Model Checking and Diagnostics for Statistical Analyses

1. Example SAS code for the primary efficacy analysis of the primary endpoint (Model 1)

```
ODS OUTPUT LSMeans= OUTLIBNAME.LSMeans SLICES= OUTLIBNAME.Diffs;
PROC MIXED DATA= INDATA;
  CLASS USUBJID TRT01PN REGION METFORMIN AGEGR1 AVISITN;
  MODEL CHG = BASE TRT01PN REGION METFORMIN AGEGR1 AVISITN
    TRT01PN*AVISITN BASE*AVISITN /DDFM =KR ;
  REPEATED AVISITN/SUB=USUBJID TYPE=UN;
  LSMEANS TRT01PN*AVISITN/SLICE=AVISITN CL DIFF;
  ESTIMATE 'Treatment difference at Week 26'
    TRT01PN 1 -1
    TRT01PN*AVISITN 0 0 0 0 1
                  0 0 0 0 -1 /CL ;
RUN;
```

2. Example SAS code for the supportive analysis – interaction terms- of the primary endpoint

For HbA1c (Baseline HbA1c category: HBGR1):

```
ODS OUTPUT LSMeans= OUTLIBNAME.LSMeans SLICES= OUTLIBNAME.Diffs;
PROC MIXED DATA= INDATA;
  CLASS USUBJID TRT01PN REGION METFORMIN AGEGR1 AVISITN HBGR1;
  MODEL CHG = HBGR1 TRT01PN REGION METFORMIN AGEGR1 AVISITN
    TRT01PN*AVISITN HBGR1*AVISITN TRT01PN*HBGR1
    TRT01PN*HBGR1*AVISITN /DDFM =KR ;
  REPEATED AVISITN/SUB=USUBJID TYPE=UN;
  LSMEANS TRT01PN*HBGR1*AVISITN/SLICE=AVISITN CL DIFF;

  ESTIMATE 'Treatment difference at Week 26 for Baseline HbA1c
  Category < 8.0%'
    TRT01PN 1 -1
    TRT01PN*AVISITN 0 0 0 0 1 0 0 0 0 -1
    TRT01PN*HBGR1*AVISITN 0 0 0 0 0 0 0 0 1 0
                          0 0 0 0 0 0 0 0 -1 0 /CL ;
RUN;
```

(or use the following statement to replace the 'LSMEANS' AND 'ESTIMATE' statements above:
SLICE HBR1*TRT01PN*AVISITN/SLICEBY(AVISITN='26') DIFF; and ODS table SLICETESTS to obtain p-value for the interaction at Week 26 (AVISITN=26).

For Age category, Metformin use or Region:

```
ODS OUTPUT LSMeans= OUTLIBNAME.LSMeans SLICES= OUTLIBNAME.Diffs;
PROC MIXED DATA= INDATA;
  CLASS USUBJID TRT01PN REGION METFORMIN AGEGR1 AVISITN;
  MODEL CHG = BASE TRT01PN REGION METFORMIN AGEGR1 AVISITN
    TRT01PN*AVISITN BASE*AVISITN TRT01PN*AGEGR1
    AVISITN*AGEGR1 TRT01PN*AGEGR1*AVISITN /DDFM =KR ;
  REPEATED AVISITN/SUB=USUBJID TYPE=UN;
  LSMEANS TRT01PN*AGEGR1*AVISITN /SLICE=AVISITN CL DIFF;

  ESTIMATE 'Treatment difference at Week 26 for Age category < 65'
    TRT01PN 1 -1
    TRT01PN*AVISITN      0 0 0 0 1 0 0 0 0 -1
    TRT01PN*AGEGR1*AVISITN 0 0 0 0 1 0 0 0 0 0
    0 0 0 0 -1 0 0 0 0 0 /CL ;
```

RUN;

Note: The contrasts may need to be adjusted for a different factor.

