(or use the following statement to replace the 'LSMEANS' AND 'ESTIMATE' statements above:
SLICE HBR1*TRT01PN*AVISITN/SLICEBY(AVISITN='26') DIFF; and ODS table SLICETESTS to obtain p-value for the interaction at Week 26 (AVISITN=26).

3. Example SAS code for the by-subgroup analysis of the primary endpoint

Take by-FPG Tertiles as an example

```
ODS OUTPUT LSMeans= OUTLIBNAME.LSMeans SLICES= OUTLIBNAME.Diffs;
PROC MIXED DATA= INDATA;
  CLASS USUBJID TRT01PN REGION METFORMIN AGEGR1 FPG_TTL AVISITN;
  MODEL CHG= BASE TRT01PN REGION METFORMIN AGEGR1 FPG_TTL
    AVISITN TRT01PN*AVISITN BASE*AVISITN
    TRT01PN*FPG_TTL FPG_TTL*AVISITN
    TRT01PN*FPG_TTL*AVISITN /DDFM =KR ;
  REPEATED AVISITN/SUB=USUBJID TYPE=UN;
  LSMEANS TRT01PN*FPG_TTL*AVISITN/SLICE=AVISITN CL DIFF;
  ESTIMATE 'Treatment difference at Week 26 for 1st Baseline FPG
  Tertile'
    TRT01PN -1 1
    TRT01PN*AVISITN      0 0 0 0 1 0 0 0 0 -1
    TRT01PN*FPG_TTL*AVISITN 0 0 0 0 1 0 0 0 0 0
    0 0 0 0 0 0 0 0 0 -1
    0 0 0 0 0 0 0 0 0 0 /CL ;
```

RUN;

For Age category

Use the same SAS code for the supportive analysis on interaction terms.

For Baseline HbA1c category

```
ODS OUTPUT LSMeans= OUTLIBNAME.LSMeans SLICES= OUTLIBNAME.Diffs;
PROC MIXED DATA= INDATA;
  CLASS USUBJID TRT01PN REGION METFORMIN AGEGR1 HBGR1 AVISITN;
  MODEL CHG= HBGR1 TRT01PN REGION METFORMIN AGEGR1 AVISITN
    TRT01PN*AVISITN HBGR1*AVISITN
    TRT01PN*HBGR1*AVISITN/DDFM =KR ;
  REPEATED AVISITN/SUB=USUBJID TYPE=UN;
  LSMEANS TRT01PN*AVISITN/SLICE=AVISITN CL DIFF;
  ESTIMATE 'Treatment difference at Week 26 for Baseline HbA1c
<8.0%'
    TRT01PN -1 1
    TRT01PN*AVISITN      0 0 0 0 1 0 0 0 0 -1
    TRT01PN*HBGR1*AVISITN 0 0 0 0 1 0 0 0 0 0
    0 0 0 0 -1 0 0 0 0 0 /CL ;
RUN;
```

4. Example SAS code for key secondary efficacy endpoints Weight, Insulin dose etc (Model 2)

```
ODS OUTPUT LSMeans= OUTLIBNAME.LSMeans SLICES= OUTLIBNAME.Diffs;
PROC MIXED DATA= INDATA;
  CLASS USUBJID TRT01PN REGION METFORMIN AGEGR1 AVISITN HBGR1;
  MODEL CHG= BASE TRT01PN HBGR1 REGION METFORMIN AGEGR1 AVISITN
    TRT01PN*AVISITN BASE*AVISITN /DDFM =KR ;
  REPEATED AVISITN/SUB=USUBJID TYPE=UN;
  LSMEANS TRT01PN*AVISITN/SLICE=AVISITN CL DIFF;
  ESTIMATE 'Treatment difference at Week 26'
    TRT01PN -1 1
    TRT01PN*AVISITN 0 0 0 0 -1
    0 0 0 0 1 /CL ;
RUN;
```

Note: The contrasts may need to be adjusted for an endpoint that has a different visit scheme from that of HbA1c.

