5. Example SAS code for analysis on FPG change from baseline by baseline FPG tertiles

```
ODS OUTPUT LSMeans= OUTLIBNAME.LSMeans SLICES= OUTLIBNAME.Diffs;
PROC MIXED DATA= INDATA;
  CLASS USUBJID TRT01PN REGION METFORMIN AGEGR1 HBGR1 FPG_TTL
    AVISITN;
  MODEL CHG= FPG_TTL HBGR1 TRT01PN REGION METFORMIN AGEGR1
    AVISITN TRT01PN*AVISITN TRT01PN*FPG_TTL
    FPG_TTL*AVISITN TRT01PN*FPG_TTL*AVISITN /DDFM =KR;
  REPEATED AVISITN/SUB=USUBJID TYPE=UN;
  LSMEANS TRT01PN*FPG_TTL*AVISITN/SLICE=AVISITN CL DIFF;
  ESTIMATE 'Treatment difference at Week 26 for 1st Baseline FPG
  Tertile'
    TRT01PN -1 1
    TRT01PN*AVISITN      0 0 0 0 1 0 0 0 0 -1
```

```
TRT01PN*FPG_TTL*AVISITN 0 0 0 0 1 0 0 0 0 0  
0 0 0 0 0 0 0 0 0 0 -1  
0 0 0 0 0 0 0 0 0 0 /CL ;  
RUN;
```

5. Example SAS code for analysis on exposure-adjusted event rate with Poisson regression model

```
ODS OUTPUT LSMeans= Lsmeans Diffs=Diffs;  
proc genmod data=INDATA;  
  class USUBJID TRT01AN MCRIT2ML HBGR1 AGEGR1 METFMN CTRYGR1;  
  model NUMEVT1=TRT01AN MCRIT2ML HBGR1 AGEGR1 METFMN CTRYGR1/  
d=poisson offset=PYOFFSET;  
  repeated SUBJECT=USUBJID /corrw covb type=exch;  
  LSMEANS TRT01AN/ EXP ILINK E CL DIFF;  
run;
```

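### SAP Appendix 11 item 2 offers SLICETESTS as the Week 26 interaction p-value, but that table tests equality of all treatment-by-factor means

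*SAP*

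**What the plan says.** - **Rule.** SAP 7.1.1.2 examines treatment by baseline HbA1c category, region, age category and metformin use, one factor at a time at 0.10. Absence of a significant qualitative interaction counts in favour of the main-effects model. SAP 7.1.1.3 promises interaction p-values for the subgroup analyses. Table 2.03 is the planned Week 26 display.
- **Model.** SAP 7.1.2 describes a "supportive MMRM model that adds terms for treatment-by-variable interaction". Its specification ends "Baseline HbA_{1c}-by-Visit Week Interaction + Treatment-by-Variable + Visit Week-by-Variable + Treatment-by-Visit Week-by-Variable", and the by-subgroup model ends "Treatment-by-Visit Week-by-Variable + Treatment-by-Variable + Visit Week-by-Variable". Both send the reader to Appendix 11 for the code.
- **Code.** Item 2 first gives, for baseline HbA1c category, "LSMEANS TRT01PN*HBGR1*AVISITN/SLICE=AVISITN CL DIFF" and an ESTIMATE line. It then says "or use the following statement to replace the 'LSMEANS' AND 'ESTIMATE' statements above", gives a SLICE of factor by treatment by visit with SLICEBY on visit alone, and names "ODS table SLICETESTS to obtain p-value for the interaction at Week 26 (AVISITN=26". The instruction is repeated unchanged for age, metformin and region. For the age subgroup, item 3 says "Use the same SAS code for the supportive analysis on interaction terms".
- **Protocol.** Section 8.3.3.1 planned the check in an ANCOVA. The SAP uses an MMRM and does not list this among the changes in SAP 2.1.

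**The concern.** Slicing a three-way LS-mean by visit leaves every treatment-by-factor cell in the comparison. A test that all these means are equal rejects when the factor predicts HbA1c change or when the arms differ by a constant, even if the treatment difference is the same in every level. The 0.10 level then holds only when all the Week 26 means are equal.

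The first option does not help: LSMEANS with SLICE by visit is the same joint test, and the ESTIMATE line is labelled as a treatment difference within one category. So nothing in Appendix 11 gives a valid Week 26 interaction p-value. Table 2.03 could report an interaction that does not exist, or one whose significance reflects main effects.

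**Working it through.** **Inputs.** 337 completers per arm, SD 1.2, margin 0.3, one-sided 0.025 and 15% dropout (SAP Appendix 12); interaction level 0.10 (SAP 7.1.1.2); six regions (SAP Appendix 8). The documents give no factor or interaction effects, so all of those below are assumptions.

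**The plan's own figure.** n = 2(1.960 + 1.282)² × 1.44 / 0.09 = 336.2, so 337 per arm; 337/0.85 = 396.5, so 397 per arm and 794 in total. This reproduces.

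**Slice test with no interaction.** The rejection rate is the tail of a noncentral F with λ = Σ n_cell(μ − mean)²/1.44. For a 50:50 two-level factor with main effect d and no treatment difference, λ = 674(d/2)²/1.44 = 117.0d², on 3 and 670 df. A treatment difference of d with no factor effect gives the same λ; for region it is tested on 11 df.

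| d | λ | Factor effect d, 50:50 | Factor effect d, 70:30 (λ = 98.3d²) | Treatment difference d, region (11 df) |
|---|---|---|---|---|
| 0 | 0 | 0.100 | 0.100 | 0.100 |
| 0.05 | 0.29 | 0.127 | 0.123 | 0.113 |
| 0.1 | 1.17 | 0.212 | 0.193 | 0.155 |
| 0.2 | 4.68 | 0.541 | 0.477 | 0.352 |
| 0.3 | 10.53 | 0.863 | 0.800 | 0.668 |
| 0.4 | 18.72 | 0.983 | 0.962 | 0.909 |

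For six equal regions with no treatment difference, an SD of region means of 0.1 gives λ = 674 × 0.01/1.44 = 4.68 and a rate of 0.352; an SD of 0.2 gives 0.909. The interaction contrast (1 df, or 5 df for region) stays at 0.10 in every case. Simulation agrees: with a treatment difference alone of 0.1/0.2/0.3 the slice test rejects 0.216/0.539/0.864 and the 1-df contrast 0.099 to 0.102.

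**Real interaction of 0.3.** The difference-in-differences has SE 1.2√(4/168.5) = 0.185 and power 0.491 whatever the main effects. For the slice test λ = 2.63 + 117.0d², so at d = 0/0.1/0.2/0.3 it rejects 0.356/0.465/0.723/0.927. The two cross at d of about 0.11.

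**Baseline HbA1c category.** The example code for this factor drops continuous `BASE` and `BASE*AVISITN`; the models in SAP 7.1.2 keep baseline HbA1c. If it is dropped, the category effect is slope × gap in mean baseline. For an assumed gap of 0.8 to 0.9, slopes of −0.2/−0.3/−0.4 give effects of 0.16–0.18/0.24–0.27/0.32–0.36 and slice rates of 39–46%/69–79%/90–96%. With `BASE` kept and a linear baseline effect, simulation gives about 10%.

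**Estimability of the printed ESTIMATE lines.** A line is estimable only if adding it to the design matrix leaves the rank unchanged (columns in CLASS order, other factors at two levels).

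| Block | Rank without/with line | Fault |
|---|---|---|
| Item 2, HbA1c category | 23/24 | no treatment-by-factor coefficients |
| Item 2, age | 27/28 | no treatment-by-factor coefficients |
| Item 3, HbA1c category | 23/24 | `TRT01PN` sign opposite to `TRT01PN*AVISITN` |
| Item 3, FPG tertile | 38/39 | both faults |
| FPG change by FPG tertile ("Example SAS code for analysis on FPG change from baseline by baseline FPG tertiles") | 34/35 | both faults (row read as 30 coefficients) |

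None is estimable.

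**Other mismatches.** The SLICE line names `HBR1`, which is in no CLASS or MODEL statement. The item 3 HbA1c-category model lacks the Treatment-by-Variable term listed in SAP 7.1.2, and its LSMEANS gives no subgroup-specific difference. SAP 7.1.1.2 says qualitative, but no such test is specified, and the qualitative-interaction paper in SAP section 10 is not cited in the text.

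**The case against.** - **It is optional example code, and the model's own term tests could be used.** SLICETESTS is indeed only an option, and the term tests are valid interaction tests. But treatment-by-factor is averaged over visits and the three-way term tests change across visits, while the code and Table 2.03 ask for Week 26. SLICETESTS is the only named source of that p-value, and the caveat about adapting contrasts to another factor does not change what it tests.
- **The error is mostly cautious.** SAP 7.1.1.2 attaches no action to a significant result, so false flags only withhold support. This largely stands. The loss of power at small factor effects runs the other way. Even the correct contrast has only 49% power at an interaction of 0.3, so a non-significant result is weak support either way.
- **Other displays help.** Tables 2.06 to 2.09 and the level-specific differences and intervals in SAP 7.1.1.3 let a reader judge direction and size. That is true, but those estimates rest partly on the faulty ESTIMATE lines.
- **The assumed effects are large.** Effects of 0.3 to 0.4 equal or exceed the margin, and the plan expects no treatment difference. At 0.05 the rate is only 12.7%. The size is therefore uncertain; the mislabelling is not.
- **Some faults are cosmetic or visible.** The missing Treatment-by-Variable term is absorbed by the three-way term and does not change the fit. Non-estimable lines return no estimate, and `HBR1` must be edited before use. Correcting that name alone would still leave the wrong test.

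**Conclusion.** The concern holds. As written, the SLICETESTS option returns a joint test of equal means under the label of an interaction test, and its p-value does not measure the interaction in either direction. False flagging ranges from 10% with all means equal, through 21% at a main effect of 0.1, to 86% at 0.3 (two-level 50:50 factor, 674 completers, SD 1.2). The rates for baseline HbA1c category apply only if `BASE` is dropped as in the example code. What the test compares follows from the syntax and needs no assumption; the rates rest on assumed effects.

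The reach is limited to Table 2.03, the interaction p-values of SAP 7.1.1.3 where this code is reused, and the subgroup ESTIMATE lines. Model 1, the non-inferiority decision and the testing order are unaffected. It should be corrected, but it does not threaten the trial's main conclusion.

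**What to change.** 1. **Replace SLICETESTS** in item 2 with a Week 26 difference-in-differences CONTRAST or LSMESTIMATE on treatment by factor by visit (1 df for two-level factors, levels minus 1 otherwise, so 5 df for region). Use it for Table 2.03 and SAP 7.1.1.3, and replace `HBR1` by the factor being tested. Coefficients must follow each block's CLASS order:
   - Item 2, HbA1c category: `TRT01PN*HBGR1 1 -1 -1 1`, `TRT01PN*HBGR1*AVISITN 0 0 0 0 0 0 0 0 1 -1 0 0 0 0 0 0 0 0 -1 1`.
   - Item 2, age: `TRT01PN*AGEGR1 1 -1 -1 1`, `TRT01PN*AGEGR1*AVISITN 0 0 0 0 1 0 0 0 0 -1 0 0 0 0 -1 0 0 0 0 1`.
   - Item 3, HbA1c category as printed: `TRT01PN*HBGR1*AVISITN 0 0 0 0 1 0 0 0 0 -1 0 0 0 0 -1 0 0 0 0 1`; if Treatment-by-Variable is added as in SAP 7.1.2, also `TRT01PN*HBGR1 1 -1 -1 1`.
   - Write out the metformin and region rows in the same way.
2. **Correct the ESTIMATE lines.** Item 2: add `TRT01PN*HBGR1 1 0 -1 0` and `TRT01PN*AGEGR1 1 0 -1 0`. Item 3, HbA1c category: use `TRT01PN 1 -1` (plus `TRT01PN*HBGR1 1 0 -1 0` if that term is added), and change LSMEANS to `TRT01PN*HBGR1*AVISITN`. Both FPG-tertile blocks: use `TRT01PN 1 -1` and add `TRT01PN*FPG_TTL 1 0 0 -1 0 0`. Check that the three-way row in the FPG-change block has 30 coefficients; 31 appear in the extracted text, possibly an artefact. The corrected lines pass the rank check.
3. **Reconcile** the HbA1c-category code with SAP 7.1.2 on whether `BASE` and `BASE*AVISITN` stay. The item 2 contrast is estimable either way.
4. **State** that the contrast tests any interaction. Either drop the word qualitative from SAP 7.1.1.2 and list that change from the protocol in SAP 2.1, or specify the qualitative-interaction test.

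Cost: a few lines of code and one or two sentences. Data collection, the primary model and the testing order do not change.

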7.1.1.1. Primary Analysis on Primary Efficacy Endpoint

The primary efficacy endpoint is the change from Baseline in HbA_{1c} at Week 26. The primary analysis of the primary efficacy endpoint will be conducted using a mixed-effect model with repeated measures (MMRM) in the FA population using all available data from analysis visits. Missing data will not be imputed.

The model will include HbA_{1c} change from Baseline as the dependent variable; treatment, region (defined in [Appendix 8: Multicenter Studies and Definition of Geographic Region for Statistical Analysis](#)), age category, current metformin use, visit week, treatment-by-week interaction, and baseline HbA_{1c}-by-week interaction as fixed effects; baseline HbA_{1c} as a continuous covariate; and subject as a random effect (Model 1). Treatment effects estimates (and associated hypothesis tests) of albiglutide will be evaluated within this MMRM model as least squares means contrasts relative to insulin lispro. An unstructured covariance matrix will be used for the MMRM analysis, unless the model does not converge, in which case the covariance matrix will be decided upon model convergence status and the Akaike information criterion (AIC). The MIXED procedure in SAS will be used to implement the MMRM analysis. The least squares means (and standard errors) of HbA_{1c} at each study visit and least squares means (and standard errors) of change from Baseline in HbA_{1c} at each postbaseline study visit will be presented. The least squares mean and the associated 1-sided 97.5% confidence interval of the treatment difference in change from Baseline in HbA_{1c} at each postbaseline study visit will be reported. In addition, the observed HbA_{1c} and change from Baseline HbA_{1c}

will be summarized descriptively. The least squares means (and standard errors) of change from Baseline HbA_{1c} will be plotted by treatment group.

The null hypothesis will be tested based on the 1-sided 97.5% confidence interval of the least squares mean of the treatment difference at Week 26 estimated from the MMRM model. If the upper bound of the confidence interval is less than or equal to 0.3%, non-inferiority will be concluded. If non-inferiority is established, key secondary endpoints will be tested as described in Appendix 11.10.

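### SAP 11.11.1 example code subtracts the arms in opposite orders for HbA1c and for weight and insulin dose without stating the arm coding, and several printed subgroup ESTIMATE vectors are not estimable

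*SAP*

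**What the plan says.** **Direction in the SAP body.** SAP 7.1.1.1 says treatment effects are "evaluated within this MMRM model as least squares means contrasts relative to insulin lispro". The decision rule there is one-sided: "If the upper bound of the confidence interval is less than or equal to 0.3" (percentage points of HbA1c), non-inferiority is concluded. The figure list in SAP 11.14.5 presents the modelled HbA1c, weight and insulin-dose results as albiglutide versus lispro (Figures 2.04, 2.24 and 2.45).

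**Confirmatory contrasts in SAP 11.11.1.**
- Item 1 (Model 1, HbA1c): main effect `1 -1`; interaction "TRT01PN*AVISITN 0 0 0 0 1" for the first arm, with -1 at the same visit for the second arm.
- Item 4 (Model 2, weight and insulin dose): main effect `-1 1`; interaction -1 for the first arm and +1 for the second.

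**Subgroup contrasts in the same section.**
- Item 2 (baseline HbA1c category; age category): `1 -1` throughout, with no treatment-by-factor coefficients.
- Item 3, FPG tertile ("Treatment difference at Week 26 for 1st Baseline FPG" tertile): main effect `-1 1`, treatment-by-visit +1/-1, three-way line "TRT01PN*FPG_TTL*AVISITN 0 0 0 0 1 0 0 0 0 0" and so on. No treatment-by-tertile coefficients.
- Item 3, baseline HbA1c category: main effect `-1 1`, treatment-by-visit +1/-1, three-way line "TRT01PN*HBGR1*AVISITN 0 0 0 0 1 0 0 0 0 0" with -1 for the second arm.
- Item 3, age category: "Use the same SAS code for the supportive analysis on interaction terms", which points back to item 2.
- The first of the two items numbered 5 (FPG change by tertile): same pattern as the item 3 FPG code.

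Neither document says which arm has the lower TRT01PN value.

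**The concern.** Items 1 and 4 carry the same Week 26 label but estimate quantities of opposite sign. No single coding of TRT01PN makes both agree with the SAP body. HbA1c non-inferiority is a one-sided decision, so its direction is part of the decision. Weight and prescribed insulin dose are the first two step-down tests in SAP 11.10, so the sign of their estimates is the confirmatory message.

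The subgroup statements have a different defect. Their coefficients do not fit together, so the ESTIMATE statements cannot return the differences they are labelled with.

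**Working it through.** **1. The planning standard error.** Inputs from SAP 11.12: SD 1.2, 337 completers per arm, margin 0.3, one-sided 0.025, 90% power, 15% dropout.
- n per arm = 2 × 1.2² × (1.960 + 1.282)² / 0.3² ≈ 336.3, rounded up to 337. Then 337/0.85 = 396.5, rounded up to 397, and 2 × 397 = 794. The plan's figures are reproduced.
- SE = 1.2 × √(2/337) = 0.0924, and 1.96 × SE = 0.181. This matches the plan's minimum detectable difference of 0.18.

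**2. Items 1 and 4.** The coefficient vectors were tested against the row space of the over-parameterised design (2 arms × 5 visits). Both are estimable. Item 1 is arm 1 minus arm 2; item 4 is arm 2 minus arm 1.

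| TRT01PN first level | Item 1 (HbA1c) | Item 4 (weight, dose) |
|---|---|---|
| Albiglutide | albiglutide - lispro, as required | lispro - albiglutide, reversed |
| Lispro | lispro - albiglutide, reversed | albiglutide - lispro, as required |

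**3. If albiglutide is first.** Each weight or dose estimate d with interval (L, U) is reported as -d with (-U, -L). The two-sided p-value does not change.

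**4. If lispro is first.** Take an observed albiglutide-minus-lispro difference of +0.20.
- Correct upper bound: 0.20 + 0.181 = 0.38, above 0.3, so non-inferiority is not shown.
- Reversed upper bound: -0.20 + 0.181 = -0.02, so the rule is met.

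Probability of meeting the rule, by true difference δ: correct Φ((0.3 - δ)/SE - 1.96); reversed Φ((0.3 + δ)/SE - 1.96).

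| δ (albiglutide worse by) | Correct | Reversed |
|---|---|---|
| 0.0 | 0.901 | 0.901 |
| 0.1 | 0.581 | 0.991 |
| 0.3 | 0.025 | about 1.00 |

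**5. Estimability of the subgroup contrasts.** An estimable contrast is a combination of cell means. For each arm, the treatment coefficient must therefore equal the sum of that arm's treatment-by-visit coefficients. Where the MODEL contains a treatment-by-factor term, each of its coefficients must equal the sum over visits of the matching three-way coefficients. The printed vectors break one or both rules. The residual is the distance from the row space (0 means estimable).

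| Contrast | Residual, omitted terms set to 0 | Residual, omitted terms spread equally | What makes it 0.000 |
|---|---|---|---|
| Item 2, HbA1c category and age | 0.943 | 0.408 | add treatment-by-factor `1 0 -1 0` |
| Item 3, FPG tertile | 1.443 | 1.414 | main effect to `1 -1` and add treatment-by-tertile `1 0 0 -1 0 0` |
| Item 3, HbA1c category | 1.359 | no such term in the MODEL | main effect to `1 -1` only |
| First item 5, FPG tertile | 1.724 | 1.700 | as item 3 FPG, with 30 three-way coefficients |

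For the item 3 FPG contrast, correcting the sign alone leaves 0.866 (0.471 with equal spreading), so both changes are needed. The first item 5 shows 31 three-way coefficients where 30 are needed. With one zero dropped its residual is 1.443, so it fails either way. The extra zero may be an artefact of text extraction, and nothing here rests on it.

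**The case against.** **It is only example code, and the prose governs.** Each block is headed as an example, and SAP 2.4 and 7.1.1.1 fix the direction. A programmer who follows the text would have to correct the contrast, and the by-arm least squares means reported or plotted alongside would expose a flipped sign. This stands as mitigation. It does not remove the error: SAP 7.1.2 and 8.2.5 send the reader to this appendix for the SAS code, and its notes allow contrasts to be adjusted for a different factor or visit scheme, not for direction.

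**The serious branch depends on an unstated fact.** This stands. A reader might infer that the primary test is reversed. The documents do not support that, because it happens only if lispro is coded first. The SAP usually lists albiglutide first, which is suggestive but not proof. Nor would a reversed bound of -0.02 by itself yield a superiority claim, since HbA1c superiority is tested last, after weight and dose.

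**The subgroup differences are still available.** This also stands. A reader might infer that the subgroup results, and Table 2.06 in particular, cannot be produced. Only the ESTIMATE vectors fail. Item 2, the item 3 FPG code and the first item 5 each include a three-way LSMEANS with differences, and item 2 also offers a SLICE alternative. The item 3 HbA1c-category LSMEANS covers only treatment by visit. However, item 2's HbA1c-category code fits the same model (rank 20 in both) and supplies those differences. A non-estimable ESTIMATE should also be flagged by the software, not return a plausible wrong number.

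**Conclusion.** Wrong as written; should be fixed before database freeze. Items 1 and 4 are exact negatives under one label, so one contradicts the SAP's own direction whatever the coding.

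The size depends on the unstated coding. With albiglutide first, the damage is the sign of the weight and insulin-dose estimates and intervals; the two-sided tests stand. With lispro first, the non-inferiority bound is read in the wrong direction, with the planning-SE consequences shown above. Both branches assume the printed ESTIMATE statements are run unaltered.

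The non-estimable vectors in item 2, item 3 and the FPG-tertile item 5 are a separate code correction. They concern analyses outside the testing hierarchy, and the LSMEANS differences already supply their results.

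**What to change.** In SAP 11.11.1:
- State the TRT01PN coding, and write every contrast as albiglutide minus lispro (`1 -1` throughout if albiglutide is first; all signs reversed, including those below, if it is not).
- Add treatment-by-factor coefficients where the MODEL has that term: `1 0 -1 0` in item 2 (and so in the age subgroup, which reuses it); `1 0 0 -1 0 0` in the FPG-tertile code of item 3 and the first item 5.
- In the item 3 HbA1c-category code, correct only the main-effect sign, because that MODEL has no `TRT01PN*HBGR1` term, and change LSMEANS to `TRT01PN*HBGR1*AVISITN`.
- Check the number of three-way coefficients in the first item 5 (30 needed), and renumber the second item 5, the Poisson model.

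The cost is an edit to one appendix. Design, data and the 337 per arm are unaffected.
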